4.2. Inclusion criteria

- Female only
- UK residents, age ≥ 18
- BMI between 22.5 and 32.5 kg/m²; as approximately 70% of adults in England have a BMI within this range [25]
- Proficiency in English language
- Self-report liking each of the test foods

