7. STATISTICAL ANALYSIS

All statistical analyses will be performed using SPSS (Version 26.0). The level of significance will be set at $p < 0.05$ for primary analyses and $p < 0.01$ for secondary analyses to account for multiple testing.

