7.4. Primary analyses

7.4.1. Confirmatory analyses

To be consistent with previous studies we ran investigating the effect of SEP on intended energy consumption (e.g [45]), the primary measure of SEP used in our primary analysis will be highest educational qualification (binary – lower vs higher).

A mixed ANOVA will be used to test the effect of portion size (categorical: larger, smaller; within-subject), SEP (categorical: lower (\leq A level), higher ($>$ A level), between-subjects), the interaction portion size*SEP on daily energy intake. If the interaction between portion size*SEP is significant the analysis will be stratified by SEP (\leq A level, $>$ A level) and two repeated-measures t-tests will be used to examine the effect of portion size (larger vs smaller) on daily energy intake in the two groups of participants separately. We will not correct for multiple comparisons as we specified a priori hypotheses.

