7.4.2. Sensitivity analyses

Sensitivity analyses will be conducted to examine whether the pattern of results from the main analyses differ after 1/ excluding participants guessing the aims of the study, 2/ excluding outliers on main outcome variables (identified as those with a value $>$ 3SD from condition mean) and influential cases (identified as those with a Cook's distance $>$ 1, indicating a multivariate outlier [37], 3/

substituting SEP measure (highest educational qualification, \leq A level, $>$ A level) with alternative measures of SEP (level of education – composite score, subjective socioeconomic status (1-10), and household income).

The main analyses will also be repeated controlling for any non-SEP based demographic variables (e.g. BMI, age) that significantly differ between the higher vs. lower SEP groups in order to examine if results remain consistent. To examine whether the order that portions are presented impacts the findings, the main analyses will be repeated with an additional 2-level between-subjects factor (portion size order: smaller, larger vs larger, smaller). Finally, the main analyses will be repeated with dishware size as an additional 2-level within-subjects factor (dishware size: smaller vs larger).

We will report whether sensitivity analyses result in deviations from the pattern of significance to the main analyses (i.e., any significant differences between conditions becoming not significant, and vice versa).

Note if $>30\%$ participants guess the study aim we will include aim guessing as a between-subjects factor in ANOVA rather than use listwise removal.

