7.5. Secondary analyses

7.5.1. Mediation analyses

For each participant, we will compute the average daily energy intake in the larger portion condition minus average daily energy intake in the smaller portion size condition, referred below as the portion size effect (PSE).

We will first report and compare the individual measures of impulsivity, inhibition, portion size appropriateness, satiety responsiveness, plate clearing tendencies, perceived food insecurity, resource availability in childhood, food choice motives, and compensatory health beliefs for lower and higher SEP groups using means, standard deviations and T-tests. If we find individual differences for any of these measures between participants of lower and higher SEP, mediation analyses will be performed in order to examine the extent to which it mediates the effect of SEP on the PSE (**Figure 2**).

[figure not shown]

Figure 2. Mediation diagrams for the PSE. Indirect effect of SEP on the PSE through a mediator M = $c - c' = ab$.

The mediation will be tested by estimating the indirect effects of SEP on the PSE through all the potential mediators and testing their indirect effect using bias-corrected bootstrap. We will use the PROCESS macro (Model 4 – one mediator at a time and all together) in SPSS that provides asymmetric bias-corrected bootstrap confidence intervals for inference about the indirect effects using 5,000 bootstrap samples [38]. Mediation will be tested by determining whether or not the confidence intervals of the indirect effects estimates contain zero.

If we do not find evidence that the PSE is moderated by SEP or that our individual difference measures do not explain moderation by SEP, we will repeat the primary analysis replacing SEP with the individual measures, to examine whether any of the individual difference measures moderates the main effect of portion size on daily energy intake.

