7.6. Sample size

In a previous study that used the same basic methodology but investigated the PSE over a 5-day period [39], the main effect of portion size on daily energy intake was partial $\eta^2 = 0.41$ – considered a statistically large effect size. From other studies examining shorter time frames, the effect of portion size on energy intake is medium-sized [7, 57]. To be conservative we will power the present study to be able to detect a small to medium size main effect of portion size on daily energy intake ($f=0.175$, $p < .05$, 85% power, within-subject correlation of 0.7 conservatively estimated from [39]), resulting in a minimum sample size of 46 participants. As there is limited evidence on the size of moderating effect of SEP on portion size, this sample size also provides adequate power to detect the same small to medium sized portion size and SEP interaction (within-between-subject interaction) on energy intake. Due to on-going COVID restrictions there is uncertainty over recruitment rates and it may be plausible to recruit more participants into the study. If it is feasible in the time frame of the project, we will aim to recruit up to a further 14 participants, resulting in a final $N=60$. This decision will be made prior to conducting any data analyses. Increasing sample size by approximately 30% would address uncertainty for power analysis parameters (e.g. a smaller than

anticipated sized effect being observed in the study) by increasing power. Furthermore, empirical estimates of sample sizes needed for reasonable power (e.g. 80%) in mediation analyses indicate that a sample of ≈ 60 would be sufficient to detect mediation through pathways that are medium and above in statistical size using bias-corrected bootstrap tests [40].

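### Section 7.4.2 sets no centring rule for continuous covariates and SEP measures, so its re-runs could show the portion main effect losing significance purely because of where zero lies on the scale

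*Combined protocol and SAP*

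**What the plan says.** The primary model (7.4.1) is a mixed ANOVA of daily energy intake with portion size within subjects, binary SEP between subjects, and their interaction. Three later analyses reuse it.

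- **Alternative SEP measures (7.4.2), unconditional.** Binary education is replaced by an education composite, subjective status scored 1-10, and household income.
- **Demographic adjustment (7.4.2), conditional.** "The main analyses will also be repeated controlling for any non-SEP based demographic variables", with BMI and age as examples, applies only to variables that differ significantly between the SEP groups.
- **Moderator fallback (7.5.1), conditional.** If SEP does not moderate the portion effect, or the individual measures do not explain its moderation, "we will repeat the primary analysis replacing SEP with the individual measures", in order to see whether any of them moderates the portion effect.

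For the sensitivity analyses, 7.4.2 undertakes to report deviations in the pattern of significance, described as "any significant differences between conditions becoming not significant, and vice versa". Section 7 names the software (SPSS 26). The plan does not mention centring, the covariate value at which the portion effect is evaluated, or whether a portion-by-covariate term accompanies BMI or age.

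**The concern.** When a continuous variable enters a repeated-measures model together with its interaction with portion size, the term labelled as the portion main effect is the portion effect for a participant whose value on that variable is zero. Eligibility requires "BMI between 22.5 and 32.5" kg/m² and age 18 or over, and subjective status starts at 1, so for these variables zero describes nobody in the trial. The test extrapolates far outside the data and its standard error grows accordingly.

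The portion main effect is the first hypothesis in section 2 and the effect on which section 7.6 bases the sample size. Section 3 defines the conditions as the larger and smaller portions, so the deviation rule in 7.4.2 applies directly to this effect. An uncentred re-run could therefore lead the report to say that the portion effect does not survive adjustment, or depends on the SEP measure, when only the origin of a scale has changed.

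**Working it through.** **1. The plan's own figure.** Inputs from 7.6: f = 0.175, r = 0.7, alpha 0.05, N = 46 (possibly 60), two conditions (m = 2). With λ = f²·N·m/(1 − r), λ = 0.030625 × 46 × 2 / 0.3 = 9.39. On 1 and 44 degrees of freedom, power is 85.0%, and 46 is the smallest N reaching 85%. At N = 60, λ = 12.25 and power is 93.1%.

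**2. What an uncentred variable does.** With two conditions, the within-subject part of the model is a regression of each person's difference (larger minus smaller) on the between-subject terms: D = β₀ + β₁x + error. The portion test is the test of β₀. With x centred, Var(β₀) = σ²/N. Uncentred, it is about (σ²/N)·[1 + (mean/SD)²], so λ is divided by that bracket. This takes the portion effect as unrelated to x.

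**3. Where the interaction comes from.** For a continuous SEP substitute, the portion-by-SEP term is part of the 7.4.1 model being repeated. For BMI and age it is present only if the software adds it, which the documents do not state.

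**4. BMI, with no distribution assumed.** Inside 22.5-32.5, SD² ≤ (mean − 22.5)(32.5 − mean). Mean/SD is smallest at mean = 2 × 22.5 × 32.5 / 55 = 26.59, where SD = √(4.09 × 5.91) = 4.92 and mean/SD = 5.41. The bracket is 1 + 5.41² ≈ 30.25, a 5.5-fold larger standard error. Then λ = 9.39/30.25 = 0.31, and power is at most 8.5% at N = 46 and 9.6% at N = 60. If BMI were uniform (mean 27.5, SD 2.89), the bracket is 91.5 and power is 6.1% and 6.5%.

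**5. Other variables.** The documents give no means or SDs for these, so all are assumptions.

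| Variable | Assumed mean, SD | Bracket | Power, N = 46 | Power, N = 60 |
|---|---|---|---|---|
| Subjective status | 5.5, 1.7 | 11.5 | 14% | 17% |
| Subjective status | 5.5, SD 1.5 to 2.6 | 14.4 to 5.5 | 12% to 25% | 15% to 31% |
| Age | mean/SD 2.8 to 2.3 | 8.8 to 6.4 | 17% to 22% | 21% to 27% |
| Education coded 1-9 | 5, 2 | 7.25 | 20% | 25% |
| Household income | SD/mean 0.5 to 1 | 5 to 2 | 27% to 56% | 34% to 68% |

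With the variable centred, power stays at 85% and 93%.

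**6. How often significance would be lost.** Simulation at N = 46, uniform BMI, portion effect unrelated to BMI: the portion effect was significant in 85% of runs unadjusted, 85% with centred BMI and 6% with uncentred BMI. Significance was lost in 80% of all runs uncentred (80/85 = 94% of those significant unadjusted), against 0.2% centred. With subjective status (5.5, SD 1.7), about 84% of significant effects were lost uncentred, against under 0.5% centred.

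**7. When the loss is smaller.** If the portion effect truly falls by 0.3 SD of the within-person difference per SD of BMI, significance is lost in 33% of runs rather than 80%. If the effect were as large as the partial η² of 0.41 that 7.6 cites from the 5-day study, λ = 46 × 0.41/0.59 = 32.0. Uncentred power at N = 46 is then 7-13% (BMI, mean 27.5, SD 2-4), 46-59% (age), 31-66% (subjective status) and 70-97% (income).

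**8. What does not change.** Since β₀ + β₁x = (β₀ + β₁c) + β₁(x − c), centring at c moves only the intercept. The interaction coefficient and its test are identical. In the BMI simulations the portion-by-SEP p-value was the same with and without centring in every run.

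**The case against.** The strongest reply is that the plan never says variables will be entered uncentred. A reader might infer that the re-runs will falsely report the portion effect disappearing, but the text does not support that. A model with the covariate as a main effect only, a contrast evaluated at the covariate mean, or grouped income and education would all be consistent with 7.4.2 and would avoid the problem. This stands: the defect is an omission, and its consequence is conditional.

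A reader might also infer that the SEP hypothesis or the moderator analyses are compromised. They are not. Portion by SEP, portion by continuous SEP and portion by moderator do not depend on centring, and the primary ANOVA contains no covariate. The stated purpose of the 7.5.1 fallback is moderation, and the deviation rule sits in 7.4.2, so only a portion main effect reported from those fallback models would be exposed.

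The BMI case, which has the largest loss, arises only if BMI differs significantly between SEP groups. Age is less likely to trigger adjustment because recruitment aims for equal age proportions in each education group (4.1). The size of the loss also varies widely between variables.

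These points narrow the scope without removing the issue. The subjective-status re-run is unconditional, its score cannot be zero, and entering it as a continuous measure in the plan's own model brings the interaction with it. Running that analysis directly, without centring, gives a misleading main-effect line that the plan has undertaken to interpret.

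**Conclusion.** The concern holds in a limited form. Section 7.4.2 repeats a model with continuous variables, interprets changes in significance, and does not fix where the portion main effect is evaluated. If the variables enter uncentred with their portion interaction, power for that effect at N = 46 falls from 85% to at most about 8.5% (BMI), about 14% (subjective status, assumed mean 5.5, SD 1.7) or 17-22% (age, assumed mean/SD 2.3-2.8). These figures rest on the plan's f = 0.175 and r = 0.7 and on a portion effect unrelated to the covariate. Only the BMI bound is free of an assumed distribution. For BMI and age the result also depends on software behaviour that the documents do not describe.

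The harm is confined to the portion main-effect line in supplementary analyses. This is a free improvement to the plan; it does not bear on the primary result.

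**What to change.** Add to 7.4.2, and to 7.5.1 for any portion main effect reported there:

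> Continuous covariates, continuous SEP measures and moderators are centred at the sample mean before entry, and the portion main effect is reported at that mean.

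If a measure is meant to enter in groups, or a covariate as a main effect only, state that for the re-run concerned. The cost is one sentence: no extra data, no degrees of freedom, and no change to any interaction test.

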4. PARTICIPANTS AND RECRUITMENT

4.1. Recruitment

Recruitment advertisements will be placed on social media (Facebook, Instagram, Twitter), online noticeboards (Gumtree, Call for Participants), and University of Liverpool (and other local universities') staff and students announcements and mailing lists. Flyers and posters will be distributed around the University of Liverpool campus, and if needed in local businesses and via letterbox drops in local residences with a particular focus on the most deprived areas based on the Index of Multiple Deprivation (IMD). Participants will be reimbursed for their time and expenses (£70 at the end of the study).

Recruitment will be stratified by highest educational qualification achieved or currently studying for as follows:

- 50% lower qualification levels

- No formal qualifications
- 1–3 GCSEs or equivalent
(*Level 1: first certificate; GCSE – grades 3, 2, 1 or grades D, E, F, G; level 1 award; level 1 certificate; level 1 diploma; level 1 ESOL; level 1 essential skills; level 1 functional skills; level 1 national vocational qualification (NVQ); music grades 1, 2 and 3*)
- 4+ GCSEs or equivalent
(*Level 2: CSE – grade 1; GCSE – grades 9, 8, 7, 6, 5, 4 or grades A*, A, B, C; intermediate apprenticeship; level 2 award; level 2 certificate; level 2 diploma; level 2 ESOL; level 2 essential skills; level 2 functional skills; level 2 national certificate; level 2 national diploma, level 2 NVQ; music grades 4 and 5; O level – grade A, B or C*)
- A level or equivalent
(*Level 3: A level; access to higher education diploma; advanced apprenticeship; applied general; AS level; international Baccalaureate diploma; level 3 award; level 3 certificate; level 3 diploma; level 3 ESOL; level 3 national certificate; level 3 national diploma; level 3 NVQ; music grades 6, 7 and 8; tech level*)
- 50% higher qualification levels
 - Certificate of higher education (CertHE) or equivalent
(*Level 4: certificate of higher education (CertHE); higher apprenticeship; higher national certificate (HNC); level 4 award; level 4 certificate; level 4 diploma; level 4 NVQ*)
 - Diploma of higher education (DipHE) or equivalent
(*Level 5: diploma of higher education (DipHE); foundation degree; higher national diploma (HND); level 5 award; level 5 certificate; level 5 diploma; level 5 NVQ*)
 - Bachelor or equivalent

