RANDOMISATION	
 ▪ Participants will be randomly assigned to receive the larger portion sizes at the first experimental session and the smaller portion sizes at the second experimental session or vice versa. ▪ A randomisation sequence will be created using Random Allocation Software [35] with a 1:1 allocation stratified by highest educational qualification (Group 1: low ≤ A level, 18-25 years; Group 2: low ≤ A level, 26+ years, Group 3: ≥ degree, 18-25 years, Group 4: ≥ degree, 26+ years). ▪ The allocations will be placed inside envelopes for each group; the envelopes will be sequentially opened each time a participant from one group consent to take part in the study. ▪ Participants' two experimental sessions should take place on the same day of the week
STUDY DAY 1	
 ▪ Remind allowed food / drink, physical activity restriction and install the FitBit ▪ Sleep, mood, and hunger ratings ▪ Breakfast 30 minute session between 7 am and 10:30 am ▪ Snack box 
 ○ Provide the snack box after breakfast ▪ Lunch 30 minute session (between 12pm and 2pm) ▪ Dinner 30 minute session (between 5pm and 7pm – at least 4 hours after lunch) ▪ Organise the following steps: 
 ○ Remind the date of the next session (washout)
WASHOUT SESSION	
 ▪ Participants return FitBit device and snack box ▪ Check if any additional foods/drinks consumed ▪ Remind participants about date of next session (Study Day 2)

STUDY DAY 2	
 ▪ Remind allowed food / drink, physical activity restriction and install the FitBit ▪ Sleep, mood, and hunger ratings ▪ Breakfast 30 minute session between 7 am and 10:30 am ▪ Snack box 
 ○ Provide the snack box after breakfast ▪ Lunch 30 minute session (between 12pm and 2pm) ▪ Dinner 30 minute session (between 5pm and 7pm – at least 4 hours after lunch) ▪ Organise the following steps: 
 ○ Remind the date of the next session (final session)

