7.1. Participant's characteristics

A table will present the baseline characteristics. The table will include gender, age, ethnic group, employment status, highest educational qualification, years in higher education, household income, subjective socioeconomic status and BMI for all the participants and for lower and higher education groups. Continuous variables will be summarised using means and standard deviations. Categorical variables will be summarised using counts and percentages. We will test for baseline differences between SEP groups (higher vs lower) on demographic variables using t-tests (or if data does not meet parametric assumptions – i.e. not normally distributed – Wilcoxon Mann-Whitney tests will be used) and chi-square tests.

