7.2.2. Independent variables

Socioeconomic position (SEP) will be derived from highest educational qualification, coded as lower (1 = No formal qualifications; 2 = 1–3 GCSEs; 3 = 4+ GCSEs; 4 = A level) or higher (5 = Certificate of higher education (CertHE); 6 = Diploma of higher education (DipHE); 7 = Bachelor; 8 = Master’s degree; 9 = Doctorate).

Impulsivity. Items from the Barratt Impulsiveness Scale will be coded from 1 to 4. The higher the summed score for all items, the higher the level of impulsiveness (min. = 30, max. = 120). McDonald’s Omega will be calculated as an indicator of internal consistency.

Inhibition. For correct responses, the median reaction times (RTs) in incongruent and congruent trials will be calculated [53,54]. The difference in median RTs between incongruent vs congruent trials will be calculated [incongruent RT – congruent RT] = *The Stroop interference effect*. Higher scores indicate poorer response inhibition.

Portion size appropriateness. For each participant the average selected portion size will be calculated in kcal.

Satiety responsiveness. Items will be coded from 1: *strongly disagree*, to 5: *strongly agree* and their mean will be calculated. A higher score indicates a higher satiety responsiveness. McDonald’s Omega will be calculated as an indicator of internal consistency.

Plate clearing tendencies. Response options range from 1 to 5: 1 = strongly disagree, to 5 = strongly agree. Responses will be averaged. Higher scores indicate higher plate clearing tendencies. McDonald’s Omega will be calculated as an indicator of internal consistency.

Perceived food insecurity. Based on the recommendations of the authors of the questionnaire [55] responses to the 6 questions about food insecurity will be coded as affirmatives (i.e. “yes”, “often true”, “sometimes true”, “almost every month”, “some months but not every month”) and negatives (i.e. “no”, “never true”, “only 1 or 2 months”). Coding of food security is based on the number of affirmatives as follows: 0-1 = “food secure”, 2-4 = “food insecure without hunger”, 5-6 = “food insecure with hunger”. The responses “don’t know” and blank responses reflect missing data, which will be imputed following best practice guidance [55].

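### Demographic adjustment of the non-randomised SEP contrast is run only if a low-powered baseline significance test fires, so an adjusted interaction estimate may never be reported

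*Combined protocol and SAP*

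**What the plan says.** What is randomised is the order of the portion sizes: "Participants will be randomly assigned to receive the larger portion sizes at the first experimental session" and the smaller at the second, or the reverse (Section 6, Table 2). SEP is not randomised: "Socioeconomic position (SEP) will be derived from highest educational qualification" (Section 7.2.2), dichotomised at A level, with recruitment aimed at "50% lower qualification levels" and 50% higher (Section 4.1).

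The confirmatory mixed ANOVA tests portion size, SEP and "the interaction portion size*SEP on daily energy intake" (Section 7.4.1). It has no covariates.

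Demographic adjustment appears only among the sensitivity analyses in Section 7.4.2. The sentence begins "The main analyses will also be repeated controlling for any non-SEP based demographic variables (e.g. BMI, age" and limits the set to those "that significantly differ between the higher vs. lower SEP groups". The tests are those of Section 7.1: "We will test for baseline differences between SEP groups (higher vs lower) on demographic variables using t-tests", with Mann-Whitney or chi-square tests where appropriate. BMI and age are examples; no closed list is given.

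The alpha for this screen is not stated. Section 7 says "The level of significance will be set at $p < 0.05$ for primary analyses" and sets 0.01 for secondary analyses, without saying which covers the baseline comparisons.

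**The concern.** The distinctive hypothesis in Section 2 is that the portion size effect (PSE: intake on the larger-portion day minus intake on the smaller-portion day) is greater in lower SEP. That compares two self-formed groups, so any variable that differs between them and also predicts the PSE can create or hide an interaction. By planning an adjusted re-run the sponsor accepts this possibility. The weakness is the trigger. With 23 or 30 per group, a non-significant baseline test does not show that the groups are alike, and how far a covariate biases the interaction depends on the size of the imbalance and its relation to the PSE, not on the baseline p-value. If the test does not fire, the reader gets an unadjusted interaction with no adjusted estimate beside it.

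The within-person effect of portion size is not in question; each woman is her own control.

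**Working it through.** **1. The plan's own figure.** Inputs (Section 7.6): f = 0.175, within-subject correlation 0.7, alpha 0.05, two conditions. The noncentrality is λ = f² × N × 2 / (1 − 0.7). At N = 46, λ = 0.030625 × 46 × 2 / 0.3 = 9.39. The noncentral F with 1 and 44 df gives 85.0% power for the interaction; N = 45 gives 84.2%. The stated 46 reproduces. N = 60 gives 93.1%. The 50:50 recruitment gives 23 or 30 per SEP group.

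With two conditions, the interaction test is a two-sample t-test of SEP on the PSE, so the powered effect is 2 × √(λ/N) = 2 × √(9.39/46) = 0.90 SD of the PSE.

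**2. What the screen needs in order to fire.** The observed standardised difference must exceed t(0.975, 2n − 2) × √(2/n), two-sided.
- n = 23: 2.015 × 0.295 = 0.59 SD
- n = 30: 2.002 × 0.258 = 0.52 SD
- At alpha 0.01: 0.79 and 0.69 SD

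**3. How often it fires.** Noncentral t with noncentrality d × √(n/2), where d is the true imbalance in SD:

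| d | 23 per group | 30 per group |
|---|---|---|
| 0.3 | 17% | 21% |
| 0.4 | 26% | 33% |
| 0.5 | 38% | 48% |
| 0.6 | 51% | 63% |
| 0.8 | 76% | 86% |

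At alpha 0.01, 0.5 SD is flagged 17% or 24% of the time, and 0.8 SD 51% or 67%. For a binary variable, 20% versus 40% is flagged 31% or 39% of the time at alpha 0.05.

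**4. Bias left when the screen does not fire.** Assumptions: true imbalance 0.5 SD, no true SEP effect, covariate-PSE correlation r from 0.1 to 0.5. The documents give neither quantity. The bias is r times the mean observed gap, given that the gap is below the threshold (truncated normal; the lower tail is negligible):
- n = 23: (0.594 − 0.5)/0.295 = 0.32; mean gap = 0.5 − 0.295 × 0.379/0.625 = 0.32 SD; bias 0.03 (r = 0.1) to 0.16 (r = 0.5) SD of the PSE
- n = 30: (0.517 − 0.5)/0.258 = 0.07; mean gap = 0.5 − 0.258 × 0.398/0.526 = 0.30 SD; bias 0.03 to 0.15 SD

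Against the powered effect of 0.90 SD, 0.03 to 0.16 is about 3% to 18%.

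**5. False-positive rate.** Simulation under the same assumptions gives about 5% to 7.5% for the unadjusted interaction among trials where the screen does not fire (nominal 5%).

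**6. Price of always adjusting.** With two balanced covariates unrelated to the PSE, interaction power is 84.9% instead of 85.0% at N = 46, and 93.0% instead of 93.1% at N = 60. One covariate imbalanced by 0.5 SD inflates the variance by 1 + 0.5²/4 = 1.0625. Power is then 82.8% or 91.6% if it is unrelated to the PSE, and 86.1% or 93.8% if it explains 9% of PSE variance.

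**The case against.** Four points on the other side have force.

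*Control by design.* A reader might infer that the screened re-run is the only protection against confounding. The documents do not support that. Section 4.1 aims for equal proportions of 18–25 and 26+ in each education group. Section 4.2 restricts to women with BMI 22.5 to 32.5. Section 4.3 excludes current dieters, eating disorders and appetite-affecting medication. What remains is that the age split is an aim, the upper band is open-ended, and BMI is range-restricted but not balanced.

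*Size of the harm.* A reader might also infer serious error inflation. Over all trials with a 0.5 SD imbalance and r = 0.3 to 0.5, the unadjusted interaction does have a false-positive rate of about 8% to 13% at 23 per group and 9% to 16% at 30. But those trials include the ones in which the screen fires and an adjusted result is reported. The rule's own failure is confined to the rest, where the rate is about 5% to 7.5%. The correlations are assumptions, and at r = 0.1 the effect is negligible.

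*What counts as material.* The claim that the screen misses most material imbalances cannot be made without a definition, and the documents give none. Imbalances of 0.8 SD are usually caught at alpha 0.05. The Section 7.1 table will also show age, BMI and ethnic group by education group whatever the p-values.

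*BMI as a consequence of SEP.* BMI may lie on the pathway from SEP to intake, so adjusting could remove part of the effect sought. This stands as a reason not to move the adjustment into the primary model. It does not justify letting a baseline p-value decide whether the adjusted result exists.

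**Conclusion.** The point holds in a limited form. The only *analytic* control for demographic confounding of the SEP interaction depends on a test that flags a true 0.5 SD imbalance 38% (23 per group) or 48% (30 per group) of the time at alpha 0.05, and less often if 0.01 applies. These figures need only the planned sample sizes and a two-sided t-test. The consequences rest on assumptions the documents do not supply: for a 0.5 SD imbalance and r between 0.1 and 0.5, an unflagged covariate leaves bias of about 0.03 to 0.16 SD of the PSE and a false-positive rate of about 5% to 7.5%. The loss is chiefly one of information: no adjusted estimate for the contrast that most needs one. The concern is strongest for BMI and for age within the 26+ band. It does not touch the sample size, the randomised portion-size effect or the form of the primary test.

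**What to change.** In Section 7.4.2, replace the significance trigger with wording such as: *The main analysis will be repeated adjusting for age and BMI (mean-centred, each with its interaction with portion size), whether or not they differ significantly between SEP groups, and also for any other non-SEP demographic variable that shows an imbalance.*

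- State beforehand how imbalance will be judged for the other variables, by size (for example a standardised difference fixed before analysis) and not by p-value. Naming only age and BMI would drop cover that the present text gives, for instance for ethnic group.
- The interaction terms are essential: a covariate's main effect cancels from the within-person difference, so only its interaction with portion size adjusts the SEP contrast. Centring keeps the portion-size main effect interpretable.
- Keep it as a sensitivity analysis, because of BMI's possible place on the SEP pathway.
- Report the adjusted interaction estimate with its confidence interval beside the unadjusted one. Section 7.4.2 now commits only to reporting changes in significance.

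Cost: a change of wording and two residual degrees of freedom in one sensitivity model, plus those for any further covariate. Age and BMI are already collected, and the primary test is unchanged.
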